2.3.2 KNOWN POTENTIAL BENEFITS

There is no known benefit of administering GRF6021 to patients undergoing THA or TKA.

3 OBJECTIVES AND PURPOSE

The primary objective of the study is to investigate the effect of GRF6021 on intracellular signaling cascades in blood leukocytes as determined by CyTOF. Secondary objectives include the investigation of GRF6021 on clinical recovery parameters in patients undergoing primary hip or knee arthroplasty, safety and tolerability of GRF6021, and the effects of GRF6021 on plasma proteomics.

4 STUDY DESIGN AND ENDPOINTS

4.1 DESCRIPTION OF THE STUDY DESIGN

This will be a randomized, placebo-controlled pilot study conducted at a single site, Stanford University (Stanford, California, US) to investigate the effects of GRF6021, a 5% human plasma protein fraction administered by intravenous (IV) infusion, on intracellular signaling cascades in blood leukocytes in subjects undergoing primary hip or knee arthroplasty.

Approximately 45 subjects will be enrolled with the aim of having 40 evaluable subjects randomized in a 1:1 ratio to active treatment or placebo. Each subject will receive 4 infusions of 250 mL of active GRF6021 or 4 infusions of 250 mL of placebo:

- 1) 1 infusion on the day before surgery
- 2) 1 infusion on the day of surgery within 4 hours before surgery start (first incision)
- 3) 1 infusion on the day of surgery upon arrival in the postoperative care unit (within 5 hours after the first incision)
- 4) 1 infusion on the day after surgery

Each infusion will be administered over approximately 30 minutes according to Stanford Hospital standard of care, but infusion rates and infusion time may be adjusted for tolerability or other clinical reasons, as determined by the anesthesiologist and infusion nurse.

CyTOF, a multiplexed, high-content immune profiling technology, will be utilized to provide high-resolution surveillance of circulating immune cells and the response to GRF6021 infusions on surgical recovery. Additional functional and quality of life assessments will be measured at baseline and for 6 weeks after hospital discharge. For a detailed overview of the timing of study assessments and interventions, please review [Section 15 Schedule of Events](#).

The overall duration of the study/recruitment period is approximately 12 months from study initiation (i.e., following consent of first subject) to study completion (i.e., last subject, last visit). The subject participation period is approximately 7 to 12 weeks from screening through end of study, unless prematurely discontinued.

4.2 STUDY ENDPOINTS

4.2.1 PRIMARY ENDPOINT

Primary Endpoint:

- Effect of GRF6021 on intracellular signaling cascades in blood leukocytes as determined by CyTOF.

4.2.2 SECONDARY ENDPOINTS

This study is not powered to detect statistically significant differences in outcomes. Secondary endpoints will be summarized over the study period from baseline values using descriptive statistics.

Secondary Endpoints:

- Change from baseline in 3D-CAM ([Inouye 2003](#))([Appendix 1](#)).
- Time to 50% recovery of the baseline value in the SRS ([Paddison 2011](#))([Appendix 2](#)).
- End of study treatment comparison of the Western Ontario and McMaster Universities Osteoarthritis Index (WOMAC) ([Bellamy 1986](#), [Bellamy 2002](#))([Appendix 3](#)).
- Time to a score of < 12/40 on a subset of questions from the WOMAC, Pain Subscale ([Bellamy 1986](#), [Bellamy 2002](#))([Appendix 3](#)).
- Time to a score of < 18/60 on a subset of questions from the WOMAC, Physical Function Subscale ([Bellamy 1986](#), [Bellamy 2002](#))([Appendix 3](#)).
- Change from baseline in the SF-36 ([Laucis 2015](#))([Appendix 4](#)).
- Change from baseline in the BDI-II ([Beck 1996](#))([Appendix 5](#)).
- Opioid analgesic consumption during hospital stay and after discharge to end of study.
- Time to discharge.
- Perioperative outcomes (e.g., surgery duration, anesthesia duration, PACU stay duration, ASA status, EBL, type and amount of intraoperative fluids administered, type and amount of intraoperative blood products, dose and type of anesthesia (general, regional), and intraoperative opioid dose).
- Change in functional status using the ActiGraph wearable device ([ActiGraph Corporation 2019](#)) providing measurements for physical activity/function and sleep (starting at least 3 days prior to surgery and continuing until the end of the study).
- Change from baseline in clinical laboratory parameters.
- Change from baseline in vital sign measurements.
- Change from baseline in ECG.
- The effects of GRF6021 on plasma proteomics.

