7.3.3 RANDOMIZATION

Subjects will be randomized after eligibility has been confirmed.

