7.3.4 BASELINE: ON-SITE/TREATMENT

The on-site Baseline assessments will be gathered prior to the first infusion on Day 1. After the first infusion on Day 1, the subject will be discharged from the facility and come back the following morning (Day 2) for the inpatient period. The inpatient treatment period is 2 days during which each subject will receive 3 additional doses of 250 mL of their assigned treatment allocation (i.e., either GRF6021 or placebo).

Visits 3 through 5, Treatment (Days 1-3):

- Perform the following procedures on each day *prior* to administering (the first) study infusion:
 - Review AEs and concomitant medications.
 - 12-lead ECG (**Day 1 and 3 Only**).
 - Collect sample for CyTOF assessment (**Including second infusion on Day 2**).

- Obtain samples for proteomic assessments; fasting samples preferred (**Including second infusion on Day 2**).
- Collect vital signs (BP, HR, RR, and body temperature) (**Including second infusion on Day 2**).
- Targeted physical exam (**Day 1 and 3 Only**).
- Pregnancy testing for WOCBP (**Day 1 Only**).
- Administer 3D-CAM, SRS, and WOMAC (**Day 1 and 3 Only**).
- ActiGraph device data collection (**Day 1 and 3 Only**).
- Administer study treatment per the GRF6021 Infusion Administration Manual:
 - On the day before surgery (**Day 1**).
 - On the day of surgery within 4 hours before surgery start (first incision) (**Day 2**).
 - On the day of surgery upon arrival in the PACU (within 5 hours after the first incision) (**Day 2**).
 - On the day after surgery (**Day 3**).
- Perform the following assessments following each infusion start:
 - BP and HR at 15, 30, 45, and 60 min after infusion start.
 - Body temperature and RR at 60 minutes.
 - Collection of perioperative data (**Day 2 Only**, after second infusion).
 - Opioid consumption assessment (**Days 2 and 3 Only**).
 - 12-lead ECG (**Day 3+1 Only**, after end of last infusion).
 - Exit lab panel including pregnancy test (**Day 3 Only**, after end of last infusion).
 - Administer 3D-CAM (**Day 2 Only**, after second infusion).

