7.3.6 END OF STUDY VISIT

The End of Study Visit will be conducted remotely by phone and/or electronically.

Visit 15, End of Study (Day 44 ± 2)

- Review AEs and concomitant medications.
- Perform the following assessments:
 - SRS
 - WOMAC
 - SF-36
 - BDI-II
 - Opioid consumption assessment.
- Subject will be instructed to return the ActiGraph wearable device.

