	X ² : To be performed: Prior to each infusion, within 1 hour of infusion start: BP, HR, RR, and body temperature. After the start of each infusion, at 15, 30, and 45 minutes: BP and HR. At 60 minutes after infusion start: BP, HR, RR, and body temperature.
	X ³ : To be performed following final infusion on Day 3.
	a: Preoperative infusion on the day of surgery.
	b: Postoperative infusion on the day of surgery.
	c: Screening lab panel: Alkaline phosphatase, ALT, AST, bicarbonate, bilirubin (total), ionized calcium, chloride, creatinine, GGT, glucose (random), lactate dehydrogenase, magnesium, phosphate, potassium, protein total, sodium, blood urea nitrogen, albumin, PTT, PT/INR. CBC with differential (basophils, eosinophils, lymphocytes, monocytes, neutrophils). Urinalysis: blood, glucose, ketone, protein, pH, specific gravity, nitrite, leukocytes, urine creatinine, urine protein/creatinine ratio, (and reflex urine microscopy if indicated). Infectious serology (anti-HIV antibodies, anti-hepatitis B surface antigen, anti-hepatitis B core antigen, anti-hepatitis C antibodies), direct antiglobulin test, RBC antibody screen (including direct Coombs and anti-RBC antibody), serum IgA, and haptoglobin. Urine drug screen: cannabinoids, benzodiazepine, barbiturates, opiates, cocaine, amphetamines, phencyclidine.
	d: Exit lab panel performed within ~48 hours after the last infusion (Day 3): Infectious serology (anti-HIV antibodies, anti-hepatitis B surface antigen, anti-hepatitis B core antigen, anti-hepatitis C antibodies), direct antiglobulin test, RBC antibody screen (including direct Coombs and anti-RBC antibody), ALT, AST, bilirubin (total), ionized calcium, chloride, creatinine, potassium, protein total, sodium, blood urea nitrogen, PTT, PT/INR. CBC with differential (basophils, eosinophils, lymphocytes, monocytes, neutrophils). Urinalysis: blood, glucose, ketone, protein, pH, specific gravity, nitrite, leukocytes, urine creatinine, urine protein, urine protein/creatinine ratio, and reflex urine microscopy if indicated.
	e: Serum pregnancy test required at screening. Serum and/or urine pregnancy test may be used at subsequent timepoints.
	f: For proteomic assessments, fasting samples are preferred.
	g: Baseline opioid consumption assessment will be included at screening during medication history. Subsequent opioid measurements will begin following surgery on Day 2 (Visit 4b).

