6.2 Endpoints

- Primary Endpoint (analyses detailed in this SSAP):
 - Effect of GRF6021 on intracellular signaling cascades in blood leukocytes as determined by CyTOF.
- Secondary Endpoints (analyses detailed in this SSAP):
 - Change in functional status using the ActiGraph wearable device providing measurements for physical activity/function and sleep (starting at least 3 days prior to surgery and continuing until the end of the study).
 - The effects of GRF6021 on plasma proteomics.
- Secondary Endpoints (analyses detailed in the SAP [08OCT2020]):
 - Change from baseline in 3-Minute Diagnostic Interview for Confusion Assessment Method (3D-CAM).
 - Time to 50% recovery of baseline value on the Surgery Recovery Scale (SRS).
 - End of study (EOS) treatment comparison of the Western Ontario and McMaster Universities Osteoarthritis Index (WOMAC).
 - Time to a score of < 12/40 on a subset of questions from the WOMAC, Pain Subscale.
 - Time to a score of < 18/60 on a subset of questions from the WOMAC, Physical Function Subscale.
 - Change from baseline in the Short Form-36 (SF-36).
 - Change from baseline in the Beck Depression Inventory-II (BDI-II).
 - Opioid analgesic consumption during hospital stay and after discharge to EOS.
 - Time to discharge.
 - Perioperative outcomes (e.g., surgery duration, anesthesia duration, post-anesthesia care unit (PACU) stay duration, American Society of Anesthesiologists (ASA) status, estimated blood loss (EBL), type and amount of intraoperative fluids administered, type and amount of intraoperative blood products, dose and type of anesthesia (general, regional), and intraoperative opioid dose).
 - Change from baseline in clinical laboratory parameters.
 - Change from baseline in vital sign measurements.
 - Change from baseline in electrocardiogram (ECG).

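### Opioid consumption is divided at hospital discharge, which is itself an outcome; compared as two separate amounts, the periods can differ between arms through discharge time alone

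*Protocol*

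**What the plan says.** Protocol 4.2.2 defines the endpoint as "Opioid analgesic consumption during hospital stay and after discharge to end of study". SSAP 6.2 lists it as "Opioid analgesic consumption during hospital stay and after discharge to EOS", among the endpoints whose analysis is left to the separate SAP (08OCT2020). The next bullet in both lists is "Time to discharge".

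Discharge falls after allocation: "Subjects will be randomized after eligibility has been confirmed" (Protocol 7.3.3), and infusions and surgery follow. No discharge day or time is fixed. Protocol 7.3.4 says only that "The inpatient treatment period is 2 days during which each subject will receive 3 additional doses of 250 mL", the last of these on Day 3.

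The measurement period, by contrast, is tied to surgery. Footnote g of the schedule (Protocol 15.1) says "Subsequent opioid measurements will begin following surgery on Day 2 (Visit 4b", and a baseline assessment is taken at screening. Opioids are then assessed at Visits 5 and 6 to 15. Visit 15 is on Day 44 ± 2, which the schedule labels postoperative day 42. Protocol 4.1 describes functional and quality-of-life follow-up differently, as running "Additional functional and quality of life assessments will be measured at baseline and for 6 weeks after hospital discharge", but the visit schedule counts from surgery.

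On analysis, Protocol 4.2.2 and 10.2 call the secondary endpoints descriptive. Protocol 10.4.3 nevertheless plans a comparison between groups, and 10.4.1 lists inferential methods to be considered for primary and secondary endpoints. Neither document supplied defines a combined opioid total, a daily rate, a fixed postoperative window or a rule for unequal stays.

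**The concern.** Each period's length depends on when the subject goes home, and discharge can differ by arm after treatment has begun. Since the overall span runs from surgery to Visit 15, any time cut from the hospital stay is added to the post-discharge period, and the opioids taken in that time move with it.

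A lower in-hospital amount in one arm could then be read as reduced opioid use when it reflects only a shorter stay. In the other direction, a longer stay could hide a real reduction. Adjusting for baseline opioid use does not help, because the difference comes from the length of the period and not from the subjects' starting point. Purely descriptive reporting does not remove it either: a table of in-hospital consumption by arm carries the same distortion.

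**Working it through.** The documents give no figure for this endpoint (no effect size, SD, opioid dose or length of stay), so there is no planned number to reproduce. The check is whether discharge time alone can create a difference, and how large.

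**Inputs from the documents.** Measurement starts after surgery (footnote g) and ends at postoperative day 42 (Protocol 15.1). The split is at discharge (4.2.2). The planned evaluable sample is 2 × 20 (10.5).

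**Assumptions.** Daily use is the same in both arms and declines as exp(-t/τ), with t in days from surgery and τ = 3, 7 or 14 days. Discharge is at L = 2 days in one arm and 1.5 days in the other.

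**Formulas.**
- In hospital: A(L) = τ(1 - exp(-L/τ))
- Total: T = τ(1 - exp(-42/τ)), which does not involve L
- After discharge: B(L) = T - A(L)

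**Worked case, τ = 7.**
- A(2) = 7 × (1 - 0.7515) = 1.740 and A(1.5) = 7 × (1 - 0.8071) = 1.350. The ratio is 0.776, or -22.4%.
- T = 7 × (1 - 0.0025) = 6.983, so B(2) = 5.243 and B(1.5) = 5.633. The ratio is 1.074, or +7.4%.
- T is the same in both arms.

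| τ (days) | In hospital | After discharge | Total |
|---|---|---|---|
| 3 | -19.1% | +18.1% | 0 |
| 7 | -22.4% | +7.4% | 0 |
| 14 | -23.7% | +3.9% | 0 |

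With constant use, the in-hospital change is 0.5/2 = 25%, just beyond this range.

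**Effect on a test, for illustration only.** The simulation had 20 subjects per arm, 20,000 replicates and no true difference in use. It took τ = 7 days and normal stays (mean 2.2 days, SD 0.6, floored at 1 day), independent of use. One arm was discharged half a day earlier. A two-sided t-test on log consumption was run at 0.05; the supplied documents specify no such test for this endpoint. Proportion of replicates declared significant:

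| Between-subject CV of use | In hospital | After discharge | Total |
|---|---|---|---|
| 0.4 | 0.30 | 0.08 | 0.05 |
| 0.6 | 0.20 | 0.07 | 0.05 |
| 1.0 | 0.12 | 0.06 | 0.05 |

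With no shift in discharge, all three quantities reject at about 0.05. The total counted from surgery stays at the nominal rate throughout.

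**The case against.** The strongest reply is that the documents do not show the harmful comparison to be planned. The bullet can be read as describing the coverage of one measure from the hospital stay through to end of study, and a single total is immune to the problem. The opioid analysis sits in the SAP of 08OCT2020, which may define a total or fixed windows. Protocol 10.4.1 also says endpoints will be summarised serially over time, opioid visits are scheduled from surgery, and time to discharge is reported alongside. All of this stands as a limit on the point. It does not remove it, because the wording names two periods, never says they are summed, and leaves their comparison open.

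Second, the room for early discharge is limited. The fourth infusion is given on Day 3, and evaluable subjects must have received all four. This is why a half-day shift is used above rather than a larger one. It limits the artefact but does not eliminate it, since later discharge is not bounded.

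Third, the stakes are low. The study is an unpowered pilot, and Protocol 10.2 names other endpoints (SRS, WOMAC Pain, WOMAC Physical Function) as the most important clinical outcomes. That is correct, and it sets the weight of the point.

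Three stronger readings are tempting and unsupported:
- A reader might infer that the trial is committed to testing two separate totals. The supplied documents do not say so.
- A reader might infer that GRF6021 is expected to shorten the stay. Time to discharge is only a listed endpoint, and Protocol 2.3.2 states that no benefit in these patients is known.
- A reader might infer that variation in stay between subjects biases the comparison by itself. Within arms it adds noise; a false difference needs discharge times that differ by arm.

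**Conclusion.** The point holds conditionally. If the in-hospital and post-discharge amounts are compared between arms separately, a difference in discharge time alone moves them in opposite directions. The direction of the shift and the unchanged total follow from the definition and the surgery-based schedule, and need only identical use in both arms and a common end of measurement.

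The size is illustrative: for a half-day shift from a 2-day stay, about -19% to -24% in hospital and +4% to +18% after discharge. It depends on the assumed stays and rate of decline, neither of which comes from the documents. Whether the distortion would appear in the report depends on the unsupplied SAP and on whether discharge times differ. For a secondary, mainly descriptive endpoint the consequence is modest, but the definition is worth tightening because the remedy costs little.

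**What to change.** In the endpoint definition, and in the separate SAP if it does not already do this:

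- Make the between-arm comparison the cumulative opioid consumption from end of surgery to Visit 15 (postoperative day 42). Intraoperative opioid dose is already listed separately under perioperative outcomes.
- Add one early window counted from surgery that uses an existing visit, for example to Visit 7 (postoperative day 4).
- Visit 7 has a ±1 day window and Visit 15 a ±2 day window, so cut the data at the nominal day using dated doses, or express them as mean daily use over the days actually covered.
- Adjust both comparisons for the screening opioid assessment.
- Add a 0-24 h window only if timed inpatient dose records exist. The documents do not show that they do.
- Keep the in-hospital and post-discharge amounts as description, in the same table as length of stay.

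No new visits are needed: opioids are already assessed at screening and at Visits 4b, 5 and 6 to 15. The cost is a revised endpoint sentence and slight extra derivation work, mainly handling the visit windows. If the separate SAP already specifies a total or fixed windows, a clarifying phrase is enough.

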5 STUDY ENROLLMENT AND WITHDRAWAL

5.1 INCLUSION CRITERIA

In order to be eligible for inclusion, all subjects must meet the following criteria:

1. Men and women scheduled to undergo primary THA or TKA.
2. Aged 50-85 years at time of enrollment, inclusive.
3. Renal function as defined by estimated glomerular filtration rate (eGFR) ≥ 45 mL/min/1.73 m² using the Modification of Diet in Renal Disease (MDRD) study equation.
4. Female subjects must not be pregnant or breastfeeding. Women of childbearing potential (WOCBP) must have a negative pregnancy test at screening. WOCBP must agree to use acceptable forms of contraception ([Clinical Trial Facilitation Group](#)) prior to study entry. A woman is considered of

childbearing potential following menarche and until becoming postmenopausal (no menses for at least 2 years without an alternative cause). Should a woman become pregnant or suspect she is pregnant while she or her partner is participating in the study, she should inform her treating physician immediately.

5. The subject must understand and speak English and be able to understand and follow the study procedures, receive the treatment in the established timeframe, and continue during the follow-up interval.
6. Provide a signed and dated informed consent form in accordance with local regulations and/or IRB/IEC guidelines.

5.2 EXCLUSION CRITERIA

An individual will not be eligible for inclusion if any of the following criteria apply:

1. Blood coagulation disorders, including severe liver disease, vitamin K deficiency, von Willebrand disease, hemophilia A or B or other known deficiencies in clotting factors (fibrinogen, prothrombin, factor VII, X, XI, XII, or XIII) that in the opinion of the investigator could put the subject at risk.
2. Subjects who started chronic anticoagulant therapy (warfarin, heparin, low-molecular weight heparin, or Factor Xa inhibitors) in the last 6 months. Use of pre-, intra- and post-operative anticoagulation according to standard of care is permitted. Use of antiplatelet drugs (e.g., aspirin or clopidogrel) is permitted.
3. History of a known hypercoagulable state, including Factor V Leiden thrombophilia, prothrombin gene mutation, deficiencies in antithrombin, protein C or protein S, elevated levels of fibrinogen, or dysfibrinogenemia.
4. History of deep vein thrombosis or pulmonary embolism in the last 6 months and/or if it is associated with a known hypercoagulability disorder.
5. History of disseminated intravascular coagulation, thrombotic thrombocytopenic purpura, or heparin-induced thrombocytopenia in the last 5 years.
6. Prior hypersensitivity reaction to any human blood product including plasma or a plasma protein fraction.
7. Treatment with any human blood product, including transfusions and IV immunoglobulin, during the 6 months prior to screening.
8. History of immunoglobulin A (IgA) or haptoglobin deficiency; at screening a test for IgA must be performed to confirm detectable levels of IgA.
9. History of complications of IV immunoglobulins, including stroke, anaphylaxis, or thromboembolic events.
10. History of major surgery, trauma, or injury in the last 3 months or minor surgery in the last 1 month.
11. History of unstable coronary heart disease (e.g. myocardial infarction or severe or unstable angina in the 6 months prior to dosing).
12. Moderate or severe congestive heart failure (New York Heart Association Class III or IV or metabolic equivalent < 4).
13. Uncontrolled high blood pressure (systolic blood pressure of 170 mmHg or higher and/or diastolic blood pressure of 110 mmHg or higher) despite adequate treatment during the 3 months prior to dosing.
14. Current treatment with 4 or more antihypertensive medications of different classes.
15. Clinically significant abnormalities on screening electrocardiogram (ECG) that in the opinion of the investigator could put the subject at risk, including QTc intervals (using Fridericia's correction formula) of ≥ 450 ms in men and ≥ 470 ms in women.
16. Current, active liver disease: > 3-fold elevation of liver enzymes (alanine aminotransferase (ALT)

- and aspartate aminotransferase (AST) over upper limit of normal.
17. Clinically significant abnormalities in complete blood count (CBC), complete metabolic panel, serum albumin, or coagulation.
 18. History of a major infection (e.g. bacterial pneumonia) in the last 3 months, or recent minor infection (e.g. influenza, urinary tract infection) or fever (measured body temperature above 100.5 degrees F on 2 consecutive days) that in the assessment of the Principal Investigator could interfere with the primary endpoint.
 19. Severe anemia (hemoglobin < 8 g/dL).
 20. Urine protein-to-creatinine ratio (UPCR) of > 1.5 grams of protein per gram of creatinine.
 21. Inadequate venous access to allow IV drug delivery or multiple blood draws.
 22. Concurrent participation in any other therapeutic treatment trial. If there was prior clinical trial participation, subject must have discontinued investigational agents for at least 30 days for small molecules, and 1 year for active or passive immunotherapies prior to screening.
 23. Current diseases associated with significant alterations in immune function, including, but not limited to, autoimmune disease and cancer, except adequately-treated squamous or basal-cell carcinoma.
 24. Ongoing immunosuppressant treatment or within 5 half-lives of the treatment.
 25. History of substance abuse (alcohol, drugs of abuse) in the last 2 years.
 26. Functional impairment of major joint or lower extremity other than joint undergoing surgery.
 27. Any other condition and/or situation that the investigator believes may interfere with the safety of the subject, study conduct, or interpretation of study data.

